7.4.2. Categorical Efficacy Endpoints

For the following categorical parameters, summary statistics, including sample size, frequency, and percentages will be presented.

- Proportion of participants achieving AN50/75/90/100 at Week 16
- Proportion of participants achieving HiSCR at Week 16

9. SAFETY AND TOLERABILITY

[Appendix A](#) provides a list of data displays. Sample data displays are included in a separate document.

9.1. General Considerations

The analyses in this section will be provided for the safety population in the DBVC period, OLE safety population in the OLE period, and those who applied ruxolitinib 1.5% cream throughout the study, unless otherwise specified. Summary tables may be replaced with listings when appropriate. For instance, an AE frequency table may be replaced with a listing if it only contains a few unique preferred terms reported on relatively few participants.

9.2. Adverse Events

9.2.1. Adverse Event Definitions

A TEAE is any AE either reported for the first time or worsening of a pre-existing event after first application of study drug and within 30 days of the last application of study drug. For participants who cross over treatments, the first application date is period-specific; the end date is 30 days after the last application date in this period, or the first application date in the next period, whichever comes first. Analysis of AEs (as discussed below) will be limited to TEAEs, but data listings will include all AEs regardless of their timing in relation to study drug application.

Adverse events will be tabulated by MedDRA PT and SOC. Severity of AEs will be graded using the National Cancer Institute CTCAE v5.0. The CTCAE reporting guidelines and grading details are available on the Cancer Therapy Evaluation Program website.

The subset of AEs considered by the investigator to be related to study drug will be considered to be treatment-related AEs. If the investigator does not specify the relationship of the AE to study drug, the AE will be considered to be treatment-related. The incidence of AEs and treatment-related AEs will be tabulated. In addition, serious TEAEs will also be tabulated.

Any missing onset date, causality, or severity must be queried for resolution. Unresolved missing causality and severity will be handled according to the following rules:

- An unresolved missing causality will be considered treatment-related.
- An unresolved missing severity will be identified as an unknown severity.

For purposes of analysis, all AEs will be considered TEAEs unless the AE can unequivocally be defined as not treatment-emergent.

9.2.2. Adverse Event Summaries

An overall summary of AEs by treatment group will include the following:

- Number (%) of participants reporting any TEAEs
- Number (%) of participants reporting any serious TEAEs
- Number (%) of participants reporting any Grade 3 or higher TEAEs

- Number (%) of participants reporting any treatment-related TEAEs
- Number(%) of participants reporting any ASRs
- Number (%) of participants who temporarily interrupted study treatment because of TEAEs
- Number (%) of participants who permanently discontinued study treatment because of TEAEs
- Number (%) of participants who had any fatal TEAEs

The following summaries will be produced by MedDRA term (if 2 or fewer participants appear in a table, a listing may be appropriate):

- Summary of TEAEs by MedDRA SOC and PT
- Summary of TEAEs by MedDRA PT in decreasing order of frequency
- Summary of TEAEs by MedDRA SOC, PT, and maximum severity
- Summary of TEAEs by MedDRA SOC, PT, and CTCAE grade category
- Summary of Grade 3 or higher TEAEs by MedDRA SOC and PT
- Summary of Grade 3 or higher TEAEs by MedDRA PT in decreasing order of frequency
- Summary of serious TEAEs by MedDRA SOC and PT
- Summary of serious TEAEs by MedDRA PT in decreasing order of frequency
- Summary of treatment-related TEAEs by MedDRA SOC and PT
- Summary of treatment-related TEAEs by MedDRA PT in decreasing order of frequency
- Summary of Grade 3 or higher treatment-related TEAEs by MedDRA SOC and PT
- Summary of treatment-related serious TEAEs by MedDRA SOC and PT
- Summary of TEAEs with a fatal outcome by MedDRA SOC and PT
- Summary of TEAEs leading to dose interruption by MedDRA SOC and PT
- Summary of TEAEs leading to discontinuation of study drug by MedDRA SOC and PT
- Summary of ASR by MedDRA PT in decreasing order of frequency

9.3. Clinical Laboratory Tests

The analyses in this section will be provided for the safety population in the DBVC period, as well as the OLE safety population in the OLE period, unless otherwise specified.

9.3.1. Laboratory Value Definitions

All laboratory assessments will be performed using a central laboratory, with the exception of urine pregnancy tests (as applicable). Laboratory values and change from baseline values will be summarized descriptively by visit; non-numeric test values will be tabulated when necessary. Baseline will be determined according to Section 4.1.3, using the last nonmissing value collected before the first application, prioritizing scheduled assessments for baseline identification over unscheduled visits. The last record before application in the highest priority will be considered the baseline record. For baseline laboratory candidates with the same date and time in the same priority category, additional rules may be provided after consultation with the medical monitor to delineate which value will be defined as baseline.

9.3.2. Laboratory Value Summaries

All test results and associated normal ranges from central laboratories will be reported in SI units. All tests with numeric values will have a unique unit per test. Any laboratory test results and associated normal ranges from local laboratories will be converted to SI units.

When there are multiple laboratory nonmissing values for a participant's particular test at a scheduled visit, central laboratory values have higher priority over local laboratory values. If a tie still exists, the laboratory value with the smallest laboratory sequence number will be used in by visit summaries.

For test results that will be summarized with available normal ranges, the number and percentage of participants with the laboratory values being low (but never high), normal, high (but never low) and both low and high will be calculated for each test. A shift summary will be produced for each test. The denominator for the percentage calculation will use the number of participants in the baseline category (ie, low, high, normal, or missing) as the denominator for the percentage in each of the categories during the study.

Severity grades will be assigned to laboratory test values based on the numerical component of CTCAE v5.0. Shift tables will also be presented showing change in CTCAE grade from baseline to the worst grade postbaseline. Separate summaries for abnormally high and abnormally low laboratory values will be provided when the laboratory parameter has both high and low grading criteria. The denominator for the percentage calculation will be the number of participants in the baseline category. The number of participants who experienced worsening of laboratory abnormalities will be summarized by maximum severity.

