**Table 3: Schedule of Activities (Continued)**

Visit Day (Range)	Screening	Baseline (Day 1)	Treatment (vehicle-controlled period)					Treatment (open-label extension) a				Follow-up 30 days (+ 7) days after last application		
	Days -28 to -1		Wk 2 (± 3 d)	Wk 4 (± 3 d)	Wk 8 (± 3 d)	Wk 12 (± 3 d)	Wk 16 a ± 3 d/ ET1	Wk 20 (± 3 d)	Wk 24 (± 3 d)	Wk 28 (± 3 d)	Wk 32 (± 3 d/ ET2)			
Patient-reported outcome (continued)														
Laboratory assessments														
Chemistry assessments	X	X e					X				X	X f		
Hematology assessments	X	X e					X				X	X f		
hsCRP		X			X		X				X			
FSH g	X													
Serum Pregnancy test h	X											X		
Urine Pregnancy test h		X		X	X	X	X	X	X	X				
HIV/Hepatitis Serology	X													
Translational assessments														
Photography (at selected sites)		X			X		X				X			

a All Week 16 assessments must be completed before the participant can continue in the OLE.

b Comprehensive physical examination at screening and Week 32/ET2 visit. The comprehensive physical examination will include assessment(s) of the following organ or body systems: skin; head, eyes, ears, nose, and throat; thyroid; lungs; cardiovascular system; abdomen (liver, spleen); extremities; and lymph nodes; as well as a brief neurological examination.

c A targeted physical examination may be conducted at Week 16. Targeted physical examination can be done for assessment of AE and during other visits including unscheduled visit as per discretion of the investigator. A targeted physical examination should only be conducted as indicated by symptoms reported by the participant, AEs, or other findings.

d Total HS BSA (excluding the scalp) should be ≤ 20% to be eligible for study entry and continued participation.

e Not necessary if screening assessment performed within 14 days of Day 1.

f Laboratory assessment is optional during unscheduled visits based on investigator's discretion and clinical judgement.

g Women of nonchildbearing potential only. Follicle-stimulating hormone is not needed in women with a documented hysterectomy, documented bilateral salpingectomy, or documented bilateral oophorectomy.

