## **8.7. End of Treatment and Early Termination**

The EOT coincides with the Week 32 visit. A participant that completes the Week 32 visit will have reached the EOT with study drug.

If a decision is made that the participant will permanently discontinue study drug prior to the Week 32 visit, then the ET visit should be conducted. If the ET visit coincides with a regular study visit, then the ET evaluations will supersede those of that scheduled visit, and the data should be entered in the ET page in the eCRF. If this decision does not coincide with a regular visit, reasonable efforts should be made to have the participant return to the site to complete the ET procedures.

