5.3.2. Safety Population

The safety population will include all participants who applied ruxolitinib 1.5% cream or vehicle cream at least once. Treatment groups for this population will be determined according to the actual treatment the participant applied on Day 1 regardless of assigned treatment group.

The safety population will be used for safety summaries in the DBVC period.

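### Laboratory shift percentages in SAP 9.3.2 keep participants with no post-baseline sample in the denominator, which lowers the displayed rates whenever anyone is untested (minor)

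*SAP*

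**What the plan says.** SAP 9.3.2 sets the denominator twice.

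- **CTCAE-grade shift tables:** "The denominator for the percentage calculation will be the number of participants in the baseline category". The content of the table is defined as follows: "Shift tables will also be presented showing change in CTCAE grade from baseline to the worst grade postbaseline".
- **Normal-range shift tables:** the number in the baseline category (low, high, normal or missing) serves "as the denominator for the percentage in each of the categories during the study". The on-study categories named for the accompanying summary are "low (but never high), normal, high (but never low) and both low and high will be calculated for each test". Missing is named as a baseline category but not as an on-study one.

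The laboratory analyses use the safety population in the DBVC period and the OLE safety population in the OLE (SAP 9.3). Entry to either needs only one application in the relevant period. For the first, SAP 5.3.2 says: "The safety population will include all participants who applied ruxolitinib 1.5% cream or vehicle cream at least once". No laboratory result after baseline is required.

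Protocol Table 3 schedules chemistry and hematology at screening, baseline, Week 16/ET1 and Week 32/ET2. For other occasions the footnote reads: "Laboratory assessment is optional during unscheduled visits based on investigator's discretion and clinical judgement". When a decision to stop study drug falls outside a regular visit, Protocol 8.7 says that "reasonable efforts should be made to have the participant return to the site to complete the ET procedures".

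**The concern.** A worst post-baseline grade exists only for someone with a post-baseline result. Under the stated rule, a participant without one is still counted below the line, so being untested has the same effect on the abnormality percentage as being tested and found normal.

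The schedule exposes this trial to the problem. With one scheduled draw per period there is no Week 2, 4, 8 or 12 sample to fall back on. A participant who withdraws consent or is lost to follow-up before Week 16, with no ET or unscheduled draw, has no DBVC laboratory value after baseline.

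Changes in hematology and chemistry are part of a secondary endpoint, and an initial look at safety is one of the reasons given for the sample size. Four of the six planned laboratory tables in SAP Appendix A are shift tables. With about 30 participants per arm, a few untested participants shift the percentages visibly.

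**Working it through.** The documents give no laboratory abnormality rate, dropout rate or untested fraction, so there is no stated figure to reproduce.

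**Inputs**
- About 60 participants randomized 1:1, so about 30 per arm (SAP 3.3). For illustration, all 30 are placed in one baseline category.
- One scheduled post-baseline chemistry and hematology draw per period (Protocol Table 3).
- *r*, the abnormality rate among those re-tested, and *u*, the fraction of the baseline category with no post-baseline value. Both are assumptions and are varied below.

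**Step 1: dilution within an arm.** Displayed rate = *r* × (1 − *u*).

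| *r* | *u* = 5% | *u* = 10% | *u* = 20% | *u* = 30% |
|---|---|---|---|---|
| 10% | 9.5% | 9.0% | 8.0% | 7.0% |
| 20% | 19.0% | 18.0% | 16.0% | 14.0% |

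In counts, with 5 shifts and 6 of 30 untested, the SAP rule gives 5/30 = 16.7% and a re-tested denominator gives 5/24 = 20.8%. With 3 shifts the SAP rule always shows 3/30 = 10.0%. The re-tested rate is 3/27 = 11.1% with 3 untested, 3/24 = 12.5% with 6, and 3/21 = 14.3% with 9. With nobody untested the two rules agree.

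**Step 2: difference between arms at equal *r*.** Spurious difference = *r* × (difference in *u*).
- Equal *u* (10% in each arm): 0 points.
- *r* = 20%, with 3 versus 8 of 30 untested: 0.20 × 27/30 = 18.0% and 0.20 × 22/30 = 14.7%. The gap is about 3 points, or 5.4 versus 4.4 participants.
- *u* = 5% versus 20%: 1.5 points at *r* = 10% and 3.0 points at *r* = 20%.
- *u* = 0% versus 30%: 3.0 points at *r* = 10% and 6.0 points at *r* = 20%.

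**Step 3: comparison with chance.** The standard error of a difference between two arms of 30 is √(2*r*(1 − *r*)/30), which is 7.7 points at *r* = 10% and 10.3 points at *r* = 20%. Every artefact in Step 2 is smaller than this.

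**Step 4: what is known about all treated participants.** With 5 shifts and 6 untested of 30, the rate in all 30 lies between 5/30 = 16.7% (no untested participant abnormal) and (5 + 6)/30 = 36.7% (all abnormal). The SAP percentage is the lower bound. The re-tested rate of 20.8% lies inside the range and is right for all 30 only if the untested resemble the tested.

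**The case against.** The strongest reply is that the SAP does not say how participants without a post-baseline value are displayed. The table layouts are not in these documents: SAP Appendix A refers to standard safety tables and to shells held separately. Either may contain an on-study missing column, and the list of on-study categories is not stated to be the full set of shift-table columns. With such a column the shortfall would be visible; even without one, a careful reader could recover it by subtracting the cell counts from the row total. This stands as a limit on how much is hidden. It does not change the percentage, because the denominator is specified in the text whatever columns are printed.

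Other parts of the reply also stand:

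- A reader might infer that every dropout dilutes the rates. The documents do not support that. Protocol 7.1.2 and 8.7 call for an ET visit, ET1 and ET2 include chemistry and hematology, and unscheduled draws are possible. Only participants with none of these are affected.
- A reader might infer that the arms will be made to differ. That needs unequal untested fractions, and the documents give none. Discontinuation rules tied to worsening disease make unequal discontinuation plausible, but not unequal testing.
- Protocol 10.4.3 plans no formal group comparison of laboratory data.
- The shift tables are not the only laboratory output. By-visit summaries carry the number of observations, worsening is summarized as a number of participants, abnormal values are listed, and clinically meaningful abnormalities are reported as adverse events.
- Understatement is relative to the re-tested. The true rate in all treated participants is unknown, and a re-tested denominator has its own assumption.

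**Conclusion.** The point holds in conditional form. Both denominator rules in SAP 9.3.2 count participants who cannot enter an abnormal category, so the displayed percentage falls below the re-tested rate by the relative amount *u* whenever *u* is above zero. At an assumed 6 of 30 untested that is 16.7% against 20.8%. Whether *u* will be above zero is not stated. One scheduled draw per period makes it plausible, and the ET visit should keep it below the dropout rate.

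It would go too far to say that the plan understates the true abnormality rate, or that it makes the arm with more dropout look safer. The first needs knowledge of the untested. The second needs a difference in untested fractions, and even 3 versus 8 of 30 moves the comparison by only about 3 points at a 20% rate, against a standard error of about 10. No inference rests on these tables. Severity: minor.

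**What to change.** In both denominator sentences of SAP 9.3.2, define the denominator as participants in the baseline category with at least one post-baseline value for that test in the period. In each shift table, print the number with no post-baseline value for every row and arm.

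The words *in the period* matter for the OLE. Under SAP 4.1.3, the OLE safety baseline for a participant on ruxolitinib from Day 1 is the pre-treatment value, so a Week 16 result is post-baseline but does not show that the participant was tested during the OLE.

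The cost is two SAP sentences and a programming change, with no new data. Displayed abnormality rates rise slightly. Because the tested-only rate assumes that untested participants resemble tested ones, the untested count is a necessary part of the change: it lets a reader compute the bounds shown in Step 4. If the shells already contain an on-study missing column, only the denominator wording needs to change.

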9.4. Vital Signs

The analyses in this section will be provided for the safety population in the DBVC period, as well as the OLE safety population in the OLE period, unless otherwise specified. Values at each scheduled visit, change, and percentage change from baseline for vital signs, including systolic blood pressure, diastolic blood pressure, pulse, temperature, and respiratory rate will be summarized descriptively.

Normal ranges for vital sign values are defined in [Table 4](#). For participants exhibiting vital sign abnormalities, the abnormal values will be listed along with their assigned treatment group. Alert vital signs are defined as an absolute value outside the defined normal range and percentage change greater than 25%. The abnormal values for participants exhibiting alert vital sign abnormalities will be listed.

Table 4: Criteria for Clinically Notable Vital Sign Abnormalities

Parameter	High Threshold	Low Threshold
Systolic blood pressure	> 155 mmHg	< 85 mmHg
Diastolic blood pressure	> 100 mmHg	< 40 mmHg
Pulse	> 100 bpm	< 45 bpm
Temperature	> 38°C	< 35.5°C
Respiratory rate	> 20 breaths/min	< 8 breaths/min

10. PLANNED ANALYSES

No formal interim analysis is planned in this study.

There are 2 formal planned analyses:

- The primary analysis will occur after the primary database lock, when all participants have completed or discontinued from the DBVC period. The sponsor will be unblinded after the primary database lock; however, investigators and participants will remain blinded to the individual study treatment assignment after the primary database lock.
- The final analysis will occur when all participants have completed or withdrawn from the study.

11. CHANGES AND MODIFICATIONS TO THE ANALYSIS PLAN

All versions of the SAP are listed in [Table 5](#).

Table 5: Statistical Analysis Plan Versions

SAP Version	Date
Original	12 SEP 2023

11.1. Changes to Protocol-Defined Analyses

1. Section 2.2, Study Objectives and Endpoints

Description of change: Added the secondary endpoint, "Change from baseline to Week 16 in total AN count in anatomical areas with pre-existing AN at baseline."

Rationale for change: To further evaluate the treatment effect of ruxolitinib 1.5% cream BID in participants with HS.

11.2. Changes to the Statistical Analysis Plan

Not applicable.

APPENDIX A. PLANNED TABLES, FIGURES, AND LISTINGS

This appendix provides a list of the planned tables, figures, and listings for the Clinical Study Report. Shells are provided in a separate document for tables that are not in the most current Standard Safety Tables v1.13.

The lists of tables, figures, and listings are to be used as guidelines. Modifications of the lists that do not otherwise affect the nature of the analysis will not warrant an amendment to the SAP.

Tables

Table No.	Title	Population	Standard
Baseline and Demographics Characteristics			
1.1 Disposition			
1.1.1	Analysis Populations	All randomized	X
1.1.2.1	Summary of Participant Disposition in the DBVC Period	ITT	X
1.1.2.2	Summary of Participant Disposition in the OLE Period	OLE	X
1.1.3	Summary of Number of Participants Enrolled by Country and Site	ITT	X
1.1.4.1	Summary of Protocol Deviations in the DBVC Period	ITT	X
1.1.4.2	Summary of Protocol Deviations in the OLE Period	OLE	X
1.2 Demographics and Baseline Characteristics			
1.2.1	Summary of Demographics and Baseline Characteristics	ITT	X
1.2.2	Summary of Demographics and Baseline Characteristics	OLE	X
1.3 Baseline Disease Characteristics			
1.3	Summary of Baseline Disease Characteristics	ITT	X
1.4 Prior and Concomitant Medications			
1.4.1	Summary of Prior Medications	ITT	X
1.4.2.1	Summary of Concomitant Medications in the DBVC Period	ITT	X
1.4.2.2	Summary of Concomitant Medications in the OLE Period	OLE	X
1.5 Others			
1.5	Summary of General Medical History	ITT	X
Efficacy			
2.1 AN Count			
2.1.1	Summary and Analysis of AN Count During the Study Period	ITT	
2.1.1.2	Summary and Analysis of AN Count by Baseline AN Count During the Study Period	ITT	
2.1.1.3	Summary and Analysis of AN Count by Age Group During the Study Period	ITT	
2.1.2	Summary and Analysis of AN Count in Anatomical Areas With Pre-Existing AN at Baseline During the Study Period	ITT	
2.1.3	Summary and Analysis of Participants Achieving AN50 During the Study Period	ITT	
2.1.4	Summary and Analysis of Participants Achieving AN75 During the Study Period	ITT	
2.1.5	Summary and Analysis of Participants Achieving AN90 During the Study Period	ITT	

Table No.	Title	Population	Standard
2.1.6	Summary and Analysis of Participants Achieving AN100 During the Study Period	ITT	
2.2 Skin Pain NRS			
2.2.1	Summary and Analysis of By-Visit Skin Pain NRS Score During the Study Period	ITT	
2.2.2	Summary and Analysis of Daily Skin Pain NRS Score From Baseline to Day 28	ITT	
2.2.3	Summary of Participants Achieving \geq 2-Point Reduction From Baseline in By-Visit Skin Pain NRS Score During the Study Period	ITT (baseline Skin Pain NRS score \geq 2)	
2.2.4	Summary of Participants Achieving \geq 4-Point Reduction From Baseline in By-Visit Skin Pain NRS Score During the Study Period	ITT (baseline Skin Pain NRS score \geq 4)	
